6.7 Emergency Subject Unmasking

If unmasking of a subject becomes critical to the subject's safety, the Principal Investigator must authorize such decision. If possible, such decision must be first consulted with both the study Sponsor and the Medical Monitor. Unmasking can be achieved by opening the sealed envelope that corresponds to the randomization number assigned to the subject. The Sponsor

and the Medical Monitor must be notified within 24 hours following an emergency unmasking of any subject.

6.8 Study Medication Dispensing and Collection

For each subject fulfilling eligibility criteria and for each cohort, the clinical site staff will randomize subjects as per the randomization schedule [REDACTED] and provided to the site prior to the start of the study. A randomization number, which corresponds to a study medication kit number, will be allocated to each subject. [REDACTED]

The randomization and the study medication kit number must be allocated only on the day of the first treatment application during Baseline/Day 1. Replacement kit numbers will be provided by the Sponsor should a dispensed kit become lost or damaged.

Once all Baseline/Day 1 Visit study procedures have been completed, the site will dispense the study medication to the subject. Each subject will be given one kit [REDACTED]

Study medication will be dispensed by the Study Coordinator or another designated individual (other than the investigator(s)) at the study site.

Subjects will be instructed to return their study medication [REDACTED] to the Study Coordinator or another designated individual at the Day 14 Visit. An inventory will be conducted by the site.

Each subject will be given a copy of the study medication dosing and storage instructions.

6.9 Instructions for Eyelid Scrubs

The eyelid scrub procedure must be performed by the subject, prior to the study medication application, on both eyes each morning [REDACTED].

provided by the study site. For both cohorts, eyelid scrubs will be performed only in the morning.

Each subject will be given a copy of the eyelid scrub instructions

Eyelid Scrub Instructions

1. Wash your hands thoroughly with soap and water.

Preparation of diluted baby shampoo solution:

2

3. [REDACTED]

[REDACTED]

[REDACTED]

Now proceed with performing the eyelid scrub beginning with the right eye:

6. [REDACTED]

[REDACTED]

[REDACTED]

[REDACTED]

[REDACTED]

[REDACTED]

IMPORTANT! THE COTTON SWAB MUST NOT MAKE CONTACT WITH THE SURFACE OF THE EYE OR THE WHITE PART OF THE EYE. The only contact should be to the specified areas of the eyelid.

6.10 Instructions for Use and Application of Study Medication

The study medication must be administered to both eyelids each morning, [REDACTED], after eyelid scrubs (Cohort 1), or each morning, [REDACTED] after eyelid scrubs and each evening ([REDACTED]) (Cohort 2), from the Baseline/Day 1 Visit to Day 14 Visit.

[REDACTED]

Subjects must apply the study medication as instructed below using the supplies provided by the study site.

Study Medication Application Instructions

1. Wash your hands thoroughly with soap and water.

Preparation of study medication:

2. [REDACTED]

[REDACTED]

[REDACTED]

[REDACTED]

[REDACTED]

[REDACTED]

[REDACTED]

[REDACTED]

Now proceed with applying the study medication beginning with the right eye:

10. [REDACTED]

[REDACTED]

[REDACTED]

[REDACTED]

[REDACTED]

[REDACTED]

[REDACTED]

[REDACTED]

[REDACTED] applicator and tube, apply study medication to the left eye repeating Steps 2-16.

IMPORTANT! THE APPLICATOR SPONGE MUST NOT MAKE CONTACT WITH THE SURFACE OF THE EYE OR THE WHITE PART OF THE EYE. The only contact should be to the specified areas of the eyelid.

6.11 Compliance with Eyelid Scrubs and Study Medication

It is important to encourage the subject to be compliant with eyelid scrubs and application of study medication. Compliance of both will be captured in a subject diary. The subject will be instructed on diary completion.

6.12 Return of Study Medication by the Clinical Sites

Return of used and unused study medication by the clinical site to the study medication supplier should be performed following the completion of the last subject last visit at the site, and only after database lock and following onsite verification by the CRA.

6.13 Other Study Supplies

Sites will also be provided with:

- Sterile applicators and tubes (for study medication)
- Baby shampoo, cotton swabs, bottled water, tissues, and capped tubes (for eyelid scrubs)
- Safety scissors (for opening tube packaging)
- Subject diaries and dosing instructions
- Early Treatment Diabetic Retinopathy Study (ETDRS) charts and/or illuminator cabinet (or replacement bulb with diffuser), if needed
- Urine pregnancy tests
- [REDACTED]
- [REDACTED]
- [REDACTED]
- [REDACTED]
- Visual Analog Scale (VAS) rulers
- [REDACTED]
- [REDACTED]

Additional supplies may be provided once discussed and approved by the Sponsor.

7. STUDY PROCEDURES BY VISIT

The following sections provide a list of procedures and assessments for each study visit as outlined in the Times and Events Schedule ([Appendix 1](#)). Refer to [Appendix 2](#) for information on the methods of clinical evaluation.

██████████ Ocular examination procedures will be performed bilaterally and in the order listed for each visit.

7.1 Screening Visit (Day -7 to -3)

Prior to any study assessments, potential subjects will be identified and the Investigator (or designee) will conduct the informed consent process. The purpose of the study, the study methods (visits and assessments), risks/benefits, and subject responsibilities will be discussed. The subject's willingness and ability to participate in the study will be assessed. If the subject chooses to proceed with study participation, written informed consent and HIPAA authorization will be obtained as appropriate for local privacy regulations. The original signed document will be retained in the subject records and a copy will be provided to the subject.

Perform the following procedures and/or collect the following information in the order listed:

- Assign the screening number and record in the screening log
- Record any AEs from the time the subject signs the ICF
- Record demographic data
- Record past and current relevant medical and ophthalmic history, including previous surgery(ies)/procedure(s)
- Record current (within 30 days) use and frequency of standard of care for blepharitis (e.g. eyelid scrubs, warm compresses)
- Record prior (past 12 months for isotretinoin or any other retinoids, past 3 months for other non-ophthalmic, and past 12 months for ophthalmic medications) and concomitant medication(s)
- Perform urine pregnancy test (for females of childbearing potential)
- ██████████ ██████████ ██████████ ██████████
- Measure BCVA
- Perform eyelid evaluation using ██████████ ██████████
- Perform slit lamp biomicroscopy ██████████ ██████████
- ██████████
- ██████████
- ██████████ ██████████
- ██████████ ██████████
- ██████████ ██████████

- Measure IOP
- [REDACTED]
- Perform dilated ophthalmoscopy

Instruct the subject that they should continue with their standard of care (standard routine) until the day before the Baseline/Day 1 Visit. Subjects must not perform any eyelid scrubs or warm compresses on the morning of the next visit, Baseline/Day 1, regardless of their standard of care.

At all visits following the signature of the ICF at the Screening Visit, adverse events and changes in concomitant medications and procedures will be captured.

7.2 Baseline/Day 1 Visit

The visit will occur 3 to 7 days after the Screening Visit [REDACTED] At all visits at which it is required, morning eyelid scrubs and morning study medication application will be performed by the subject under the instructions and supervision of the site staff.

Perform the following procedures and/or collect the following information in the order listed:

- Medical/Medication History Update
- [REDACTED]
- Measure BCVA
- Perform eyelid evaluation [REDACTED]
- Perform slit lamp biomicroscopy [REDACTED]
- [REDACTED]
- [REDACTED]
- [REDACTED]
- Measure IOP
- [REDACTED]
- Instruct the subject on the proper eyelid scrub technique
- Supervise the subject as they perform eyelid scrubs [REDACTED]
- Perform eyelid evaluation [REDACTED]
- Review inclusion/exclusion criteria and determine eligibility
- Randomize eligible subjects

- Dispense study medication and additional eyelid scrub supplies
- Instruct/supervise the subject as they apply study medication
- Record adverse events
- Dispense subject diary and subject dosing instructions

Instruct the subject to perform eyelid scrubs each morning prior to the application of study medication.

However, instruct the subject to not perform eyelid scrubs or apply study medication on the morning of the next visit. Subjects must bring their study medication and study supplies to all visits.

At all subsequent visits, if the subject has performed eyelid scrubs and/or applied study medication the morning of the visit, the subject must not be evaluated that day, and should be rescheduled the next day or as soon as possible. Please consult the Sponsor or Sponsor representative for additional guidance.

7.3 Treatment/Day 4 (± 1 day) Visit

Perform the following procedures and/or collect the following information in the order listed. Morning eyelid scrubs and morning study medication application must be performed by the subject under the supervision of the study staff. The visit will occur 3 days (± 1 day) after the Baseline/Day 1 Visit [REDACTED]

- Medical/Medication History Update
- Measure BCVA
- Perform eyelid evaluation [REDACTED]
- Perform slit lamp biomicroscopy [REDACTED]
- Measure IOP
- Supervise the subject as they perform eyelid scrubs [REDACTED]
- Supervise the subject as they apply study medication [REDACTED]
- Perform eyelid evaluation [REDACTED]
- Review the subject diary for compliance
- Record adverse events

Instruct the subject to perform eyelid scrubs each morning prior to the application of study medication. However, instruct the subject to not perform eyelid scrubs or apply study

medication on the morning of the next visit. Subjects must bring their study medication to the visits. Contact the subject the day before the next visits to remind them of these requirements.

7.4 Treatment/Day 8 (\pm 1 day) and Day 11 (\pm 1 day) Visits

Perform the following procedures and/or collect the following information in the order listed. Morning eyelid scrubs and morning study medication application must be performed by the subject under the supervision of the study staff. [REDACTED]

- Medical/Medication History Update [REDACTED] [REDACTED] [REDACTED]
- [REDACTED]
- Measure BCVA
- Perform eyelid evaluation [REDACTED] [REDACTED] [REDACTED]
- Perform slit lamp biomicroscopy [REDACTED] [REDACTED]
- [REDACTED]
- [REDACTED] [REDACTED]
- [REDACTED] [REDACTED]
- Measure IOP
- Supervise the subject as they perform eyelid scrubs [REDACTED] [REDACTED]
- Supervise the subject as they apply study medication [REDACTED] [REDACTED]
- Perform eyelid evaluation [REDACTED] [REDACTED] [REDACTED]
- Review the subject diary for compliance
- Record adverse events

Instruct the subject to perform eyelid scrubs each morning prior to the application of study medication. However, instruct the subject to not perform eyelid scrubs or apply study medication on the morning of the next visit. Subjects must bring their study medication to the visit. Contact the subjects the day before the next visit (Day 14) to remind them of these requirements.

7.5 Day 14 (- 1 day)

Perform the following procedures and/or collect the following information in the order listed. Morning eyelid scrubs and morning study medication application must be performed by the subject under the supervision of the study staff. [REDACTED]

- Medical/Medication History Update

- Perform urine pregnancy test for females of childbearing potential
- [REDACTED]
- Measure BCVA
- Perform eyelid evaluation [REDACTED]
- Perform slit lamp biomicroscopy [REDACTED]
- [REDACTED]
- [REDACTED]
- [REDACTED]
- [REDACTED]
- Measure IOP
- [REDACTED]
- Supervise the subject as they perform eyelid scrubs [REDACTED]
- Supervise the subject as they apply study medication [REDACTED]
- Perform eyelid evaluation [REDACTED]
- Perform eyelid evaluation [REDACTED]
- Review the subject diary for compliance and collect it
- Collect used and unused study medication
- Record adverse events

Instruct the subject to continue to perform eyelid scrubs every morning except on the morning of the next visit (Day 28/Exit Visit). Additionally, instruct the subject to refrain from wearing contact lenses until they have completed the Day 28/Exit Visit.

7.6 Day 28/Exit Visit (\pm 2 days)

Perform the following procedures and/or collect the following information in the order listed.

- Medical/Medication History Update
- [REDACTED]
- Measure BCVA

- Perform eyelid evaluation [REDACTED]
- Perform slit lamp biomicroscopy [REDACTED]
- [REDACTED]
- [REDACTED]
- [REDACTED]
- Measure IOP
- Supervise the subject as they perform eyelid scrubs [REDACTED]
- Perform eyelid evaluation [REDACTED]
- Perform dilated ophthalmoscopy
- Record adverse events
- Utilize EDC to exit the subject

7.7 Unscheduled Visits

Additional examinations or analyses may be performed as necessary to ensure the safety of subjects during the study period. Each unscheduled visit will be documented with results of the following assessments:

- Adverse event(s) and concomitant medication(s) (if applicable)
- BCVA
- Slit lamp biomicroscopy
- IOP
- Eyelid evaluation [REDACTED]

The Investigator may perform any other examination that is regarded as appropriate.

8. SCREEN FAILURES, COMPLETION AND DISCONTINUATION

8.1 Subject Screen or Eligibility Failures

Subjects who are screen or randomization failures should not be randomized into the study. The reason for screen/randomization failure must be documented.

8.2 Subject Completion

A subject is considered to have completed the study at the end of the Day 28/Exit Visit.

8.3 Subject Early Discontinuation

A subject may be discontinued from the study prior to the final study visit at the discretion of the Investigator, Sponsor, and/or IRB. Subjects may also discontinue their participation in the study at any time for any reason of their choosing.

A subject may be discontinued from the study for the following reasons, including but not limited to:

- Serious adverse event
- Violation of eligibility criteria
- Lack of compliance with the study procedures

A subject must be discontinued from the study for the following reasons, including but not limited to:

- [REDACTED]
- Withdrawal of consent
- Subject becoming pregnant in the course of the study

Procedures for Discontinuation

If a subject is discontinued or withdraws consent, no procedures other than those which may be related to the follow-up of AEs will be required. The Investigator will document the reason for the subject withdrawal.

If a subject withdraws their consent during the 14-day Treatment Period, all efforts should be taken to complete the Day 14 Visit procedures prior to subject's exit.

If a subject is discontinued due to an AE, the status of the AE at the time of discontinuation must be documented.

For any subject that is discontinued due to an AE the Investigator must ensure that adequate medical care/treatment will be provided.

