11.4 Collection and Derivation of Efficacy Assessments

For both eyes, eyelid signs and symptoms [REDACTED]

Efficacy analyses will be primarily based on the ITT population with observed data only. To check for robustness of outcomes, missing data will be imputed using last time consistent [REDACTED] observation carried forward. Additional imputations of missing data (e.g. multiple imputation methodologies) for this early phase study may be implemented as detailed in the formal statistical analysis plan.

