7.2 Per Protocol

The per-protocol (PP) population includes subjects in the ITT population who do not have significant protocol deviations likely to seriously affect the efficacy measures of the study. Protocol deviations will be assessed prior to database lock and unmasking. Subjects in the PP population will be analyzed as treated. The t-test analyses on the composite score of eyelid margin redness, eyelid debris, and eyelid discomfort will be conducted using the PP population as an additional analysis to assess efficacy when subjects strictly comply with the protocol. In the event that the ITT and PP populations are the same, this analyses will not be performed.

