8.5 Adjustments for Multiplicity

No adjustments for multiplicity will be made for this early phase study.

9 Disposition of Subjects

Subject disposition will be presented in terms of the numbers and percentages of subjects who were randomized, completed the study, and discontinued from the study. Subjects who complete the Day 28/Exit Visit will be considered study completers. Disposition will be summarized by treatment group and for all subjects.

The total number of screened subjects with the number and percentage of screen failure subjects. The reasons for screen failure will be displayed with the percentages calculated using total number of screen failures as the denominator. The number of subjects in each of the analysis populations (ITT, PP, and Safety) will be displayed by treatment and percentages will be calculated using randomized subjects as the denominator.

The number and percentage of subjects prematurely discontinued from the study and the reasons for study discontinuation will be summarized by treatment group for all randomized subjects. The reasons for study discontinuation that will be summarized include: AE, lost to follow-up, physician decision, protocol violation, study terminated by Sponsor, withdrawal by subject, and other. A subject listing will be provided that includes the date of and reason for premature study discontinuation and masking/unmasking information.

The number and percentage of subjects with major protocol deviations will be summarized by treatment group for all randomized subjects. The protocol deviations that will be summarized include: informed consent, inclusion/exclusion and randomization, test article/study drug instillation and assignment at site, improper protocol procedures at site (missed, repeated, no per protocol), site's failure to report serious adverse event (SAE)/AE, visit out of window, subject's non-compliance with test article/study drug, subject's use of prohibited concomitant medication, subject's failure to follow instructions, and other. A subject listing will be provided that includes the date of the deviation, the deviation code, the deviation description, and the classification of whether the deviation was judged to be major or minor.

In addition, subject listings will be provided that include informed consent date, inclusion and exclusion criteria violations, and exclusions from each population.

10 Demographic and Pre-treatment Variables

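### Subjects removed for ineligibility or non-compliance have no required Day 14 assessment, so the observed-data ITT comparison can lose them and move toward a per-protocol one

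*Protocol*

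**What the plan says.** On removal, Protocol section 8.3 states: "A subject may be discontinued from the study prior to the final study visit at the discretion of the Investigator, Sponsor, and/or IRB". The optional grounds it lists are a serious adverse event, "Violation of eligibility criteria" and "Lack of compliance with the study procedures". A second list gives mandatory grounds; one entry there is redacted and plays no part in this point.

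On follow-up after removal, the Procedures for Discontinuation paragraph in the same section says that "no procedures other than those which may be related to the follow-up of AEs will be required". The one provision for efficacy data reads: "If a subject withdraws their consent during the 14-day Treatment Period, all efforts should be taken to complete the Day 14 Visit procedures". It covers withdrawal of consent and nothing else.

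On analysis, Protocol section 11.4 says: "Efficacy analyses will be primarily based on the ITT population with observed data only". Protocol 11.5.2 and SAP 8.2 agree, and both add an LOCF version as a secondary or robustness analysis. Under SAP 13.3.4 a missing component makes the composite missing. The ITT set is everyone randomised, analysed as randomised (SAP 7.1). The PP set leaves out subjects with significant deviations, is analysed as treated, and is run "as an additional analysis to assess efficacy when subjects strictly comply with the protocol" (SAP 7.2). SAP section 9 tabulates discontinuation reasons by treatment group, among them "AE, lost to follow-up, physician decision, protocol violation, study terminated by Sponsor".

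**The concern.** Ineligibility and non-compliance are neither the subject's own decision to leave nor a safety event. A subject removed on either ground may still be willing to attend, yet the protocol makes no attempt to obtain the Day 14 score. It does make that attempt for subjects who have withdrawn consent, who are usually harder to assess.

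Such a subject belongs to the ITT population by definition but contributes nothing to its main Day 14 result. If the deviation is significant, the subject is absent from the PP set too. For that subject, comparing observed-data ITT with PP at Day 14 reveals nothing about what the removal did.

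Compliance is a post-randomisation variable. With a self-applied lid product it may depend on tolerability or perceived benefit, and either could differ between arms. The primary objective is dose selection, and Protocol 11.1 says the estimates will be used to power later studies. What is at stake is therefore bias in those estimates. With no formal hypotheses, type I error is not the issue.

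**Working it through.** **Inputs from the documents.** Arm sizes are about 10 (NCX 4251 QD), 5 (placebo QD), 10 (NCX 4251 BID) and 10 (placebo BID), from Protocol 3.1. Their sum, 10 + 5 + 10 + 10 = 35, matches the stated total. Each of the three composite items is scored 0–3 (SAP 13.3), so the composite runs from 0 to 3 × 3 = 9. The readable text gives no SD, dropout rate or removal rate, and no power figure to reproduce.

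**Step 1: when the data are lost.** At Days 4, 8, 11 and 14 the lid evaluation comes before diary review (Protocol 7.3–7.5). Non-compliance found at the Day 14 diary review comes too late to remove the Day 14 score. The gap therefore concerns removals decided earlier, up to and including Day 11 or between visits.

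**Step 2: share lost per removal.**
- One of 10 in an arm is 10%; one of 5 (placebo QD) is 20%.
- One of 15 in Cohort 1 is 6.7%; one of 20 in Cohort 2 is 5%.

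**Step 3: shift in an arm mean.** Suppose *m* of *n* subjects are removed. The others have mean change μ, and the removed subjects would have averaged μ + D. The full-arm mean is [(n − m)μ + m(μ + D)]/n = μ + (m/n)D, while the observed-data mean is μ. The shift is (m/n) × D in size. Assumption: D = 1 to 3 points.

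| Removed | n = 10 | n = 5 |
|---|---|---|
| 0 | 0 | 0 |
| 1 | 0.1–0.3 | 0.2–0.6 |
| 2 | 0.2–0.6 | 0.4–1.2 |

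The direction depends on which arm loses subjects and on the sign of D. Equal shifts in both arms cancel in the active-minus-placebo difference.

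**Step 4: precision.** The 95% half-width in SD units is t(0.975, n1 + n2 − 2) × √(1/n1 + 1/n2).
- Cohort 1: 10 v 5 gives 1.18; 9 v 5 gives 1.22; 10 v 4 gives 1.29.
- Cohort 2: 10 v 10 gives 0.94; 9 v 10 gives 0.97; 8 v 10 gives 1.01.

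**Step 5: chance that it arises.** If each subject has probability q of removal before Day 14 (assumption), the chance of at least one among 35 is 1 − (1 − q)^35. This is 51% for q = 2%, 83% for q = 5% and 97% for q = 10%.

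**The case against.** Several counter-arguments have force.

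- **LOCF is planned.** A removed subject's earlier scores stay in the by-visit summaries and feed the LOCF analysis. A reader might infer that such subjects vanish from every efficacy analysis, and that is not so. LOCF is nevertheless only a partial remedy. It substitutes a pre-removal value for the Day 14 value, and the readable text does not say whether baseline may be carried forward.
- **Decisions are masked.** Investigators and sponsor do not know the allocation (Protocol 6.6, SAP 4.2). This limits deliberate selection. It does not prevent compliance itself from differing by arm because of the treatment.
- **Removals are visible.** Discontinuations and reasons are tabulated by arm (SAP section 9), so an imbalance would show. The missing scores would still be missing.
- **The mechanism is weaker for ineligibility.** Eligibility is judged on criteria reviewed before randomisation, so a treatment effect on this ground is less plausible. Lack of compliance also covers missed visits, and some of those subjects might not attend Day 14 even if asked.
- **The possible bias is small beside the noise.** With three of 10 active BID subjects removed and D = 2, the shift is 0.6 points. The 7 v 10 half-width is 1.05 SD, which is larger whenever the SD exceeds 0.6/1.05 = 0.57 points. The study is descriptive and has no pre-stated power.

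These arguments lower the importance of the point. None of them supplies the missing Day 14 assessment.

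**Conclusion.** The gap is real and narrow. A randomised subject who still consents can be removed before Day 14 for eligibility or compliance, no lid assessment is then required, and the main Day 14 comparison proceeds without that subject. This can move the comparison toward a per-protocol one.

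A reader might go further and infer that the ITT comparison becomes a per-protocol comparison. The documents do not support that. Removal on these grounds is optional. Deviators who are kept remain in ITT while leaving PP, and ITT is analysed as randomised whereas PP is analysed as treated. The two sets would hold the same subjects only if every significant deviator were removed before Day 14, which nothing requires or predicts.

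The size per removal is 0.1–0.3 points in a 10-subject arm and 0.2–0.6 points in the placebo QD arm. This rests on the assumed 1 to 3 point difference and on at least one removal before Day 14; with none, the effect is zero. The point is worth making as a cheap improvement to the dose-selection estimates. It does not invalidate the plan.

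**What to change.** Leave the discontinuation grounds and all decisions about study medication as they are. Deleting the two grounds would miss the sentences that cause the data loss and would stray into clinical management, since some eligibility criteria concern safety.

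Amend the Procedures for Discontinuation paragraph of Protocol 8.3 along these lines: every subject discontinued during the treatment period, for any reason, who still consents is asked to complete the lid and safety assessments at the scheduled Day 14 time, and at Day 28 where possible.

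In the SAP:
- include these values in the observed-data ITT analysis, as randomised;
- handle the eligibility or compliance deviation through exclusion from PP only;
- tabulate missing Day 14 composites by arm and reason.

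The cost is a few attendances at visits already in the schedule and a short amendment needing IRB approval (Protocol 13.9). If adopted after Cohort 1, it cannot recover Cohort 1 data and gives the two cohorts different follow-up rules. The report should then say so wherever the cohorts are pooled or compared.
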